4.2. Scientific Rationale for Study Design

- Assessment of critical errors from inhaler handling studies has been used in previous GSK studies using an open-label, cross-over, placebo treatment design [[van der Palen, 2016](#) [van der Palen, 2018](#)].
- In common with these previous studies, a cross-over design has been chosen for the present study. No carry-over effects were demonstrated when using this design previously [[van der Palen, 2013](#)]. This design also allows participants to act as their own control in assessing their ability to use both inhalers, as well as allowing for the screening visit (V₀) and the Visit 1 to occur on the same day, thereby reducing the inconvenience to participants of multiple study site visits. Breaks of up to 30-minutes have been included in the design to allow a degree of flexibility for the participant.
- The study will use placebo inhalers for all study assessments. This aims to remove bias from any perceived benefit a participant may have for a particular active treatment. There is also no need for participants to withhold any treatments they are receiving, and there will be no need for a washout period between the inhaler used in each Assessment Period.

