8.1.4. Willingness to continue with the inhaler

After completion of the critical errors assessment for each inhaler and the ease of use questionnaire for that inhaler, the participant will also be asked the following question using a visual analogue scale ([Appendix 5](#)): 'On a scale of 0 ~~CCI~~ to 100 ~~CCI~~ would you be willing to continue with this inhaler?'

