9.2. Sample Size Determination

A total of 114 participants will be randomly assigned to study intervention such that approximately 114 evaluable participants complete the study.

The sample size for a 2x2 crossover study is based on the formula presented by [Chow](#), 2008 and [Kung-Jong](#), 2016. To calculate the conditional odds ratio (via McNemar's) the proportion of participants who have discordant pairs (those who had at least one critical error in one inhaler but not the other) was determined based on expert advice. A panel of 5 experts was convened to consider the evidence from previous studies of similar design [[van der Palen](#), 2016; [van der Palen](#), 2018] and with consideration given to observational studies in the literature [[Khassawneh](#), 2008; [Melani](#), 2011; [Arora](#), 2014; [Chorão](#), 2014; [Takaku](#), 2017; [Ocakli](#), 2018]. A consensus view of the likely error rates that would be observed with the ELLIPTA and BREEZHALER devices was subsequently reached.

A consensus was reached that the proportion of participants who make a critical error in the ELLIPTA inhaler and not on the BREEZHALER inhaler would be 6% and the proportion of patients who make a critical error in the BREEZHALER inhaler and not on the ELLIPTA inhaler would be 20%.

Based on the discordant proportions, an odds ratio of 0.3 was calculated and a standard deviation on the log odds ratio scale of 2.785 was calculated based on GSK study 200301 [[van der Palen](#), 2016]. Based on these estimates and a two-sided Type I error rate of 5%, a total of 114 participants are required to provide 90% power. No withdrawals are expected based on previous similarly designed studies. No correlation between periods is assumed and no carry over effect is assumed based on previous evidence [[van der Palen](#), 2013]. Moreover, both inhalers will contain placebo and participants may have up to a 30-minute break after demonstrating the first inhaler.

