BREEZHALER inhalers	
CCI that is, how the ease of use is rated by the participant.
 
 ○ Variable: ease of use rating. ○ Population-summary measure: The number and percentage of participants who rate the inhaler easy to use. To test whether the ease of use was easy or difficult, a McNemar's test will be performed. 
The population-measure summary defined above will be the same way for the following variables as indicated by participants' ease of use:
 
 • Telling how many doses are left in inhaler • Learning how to use the inhaler • Handling the inhaler • Preparing the inhaler • Holding the inhaler while using it
To summarise ease-of-use for ELLIPTA and BREEZHALER inhalers	
 • Ease-of-use preference from questionnaire, that is, how the ease of use is rated CCI 
CCI
 
 ○ Variable: ease of use rating. ○ Population-summary measure: The number and percentage of participants who rate the inhaler for each category. 
The population-measure summary defined above will be the same way for the following variables as indicated by participants' ease of use:
 
 • Telling how many doses are left in inhaler • Learning how to use the inhaler • Handling the inhaler • Preparing the inhaler • Holding the inhaler while using it
To compare the willingness to continue with the ELLIPTA and/or BREEZHALER inhaler	
Willingness to continue with the inhaler using a VAS between 0 CCI to 100 CCI
 
 • Variable: Willingness to continue with the inhaler. • Population summary measure: The mean and standard deviation for willingness to continue with the inhaler will be presented for each inhaler and a comparison made between the inhalers (ELLIPTA vs. BREEZHALER). 
The mean (SD), minimum and maximum will be presented. A paired t-test will be performed comparing the mean

Objectives	Statistical analysis methods
	willingness to continue with the ELLIPTA inhaler vs. the mean willingness to continue with the BREEZHALER inhaler.

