Secondary Objective: To compare ease-of-use for ELLIPTA and BREEZHALER inhalers.	Secondary 6	
Ease-of-use from questionnaire. This will be grouped as easy [REDACTED] CCI [REDACTED] or difficult [REDACTED] CCI [REDACTED] The variables will include:
 
 a) Ease of use rating b) Telling how many doses are left in inhaler c) Learning how to use the inhaler d) Handling the inhaler e) Preparing the inhaler f) Holding the inhaler while using it. 	As for primary.	The number and percentage of participants who rate the inhaler easy to use summarised for each inhaler (ELLIPTA and BREEZHALER). A McNemar's test will be performed to compare ELLIPTA vs. BREEZHALER. This will be performed for variables a) to f).

Objective	Estimand Category	Estimand		
		Variable/ Endpoint	Intercurrent Event Strategy	Population Level Summary Measure
To summarize ease-of-use for ELLIPTA and BREEZHALER inhalers	Secondary 7	
Ease-of-use from questionnaire
 
CCI [REDACTED]
 
CCI [REDACTED]
 
CCI [REDACTED]
 
The variables will include the:
 
 Ease of use rating Telling how many doses are left in inhaler Learning how to use the inhaler Handling the inhaler Preparing the inhaler Holding the inhaler while using it. 	As for primary.	The number and percentage of participants who rate the inhaler for each category for each inhaler (ELLIPTA and BREEZHALER). This will be performed for variables a) to f).
Secondary Objective: To compare the willingness to continue with the ELLIPTA and/or BREEZHALER inhaler.	Secondary 8	
Willingness to continue with the inhaler using a visual analogue scale (VAS) between 0
 
CCI [REDACTED]
 
CCI [REDACTED]
 
CCI [REDACTED]
 
to 100
 
CCI [REDACTED]
	As for primary.	The mean and standard deviation for willingness to continue with the inhaler will be presented for each inhaler (ELLIPTA and BREEZHALER). A t-test will be performed

Objective	Estimand Category	Estimand		
		Variable/ Endpoint	Intercurrent Event Strategy	Population Level Summary Measure

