4.2.2. Main analytical approach

Comparisons made between the ELLIPTA and BREEZHALER inhaler will be based on those who fall in the S₀₀ stratum. For the full definition of the primary estimand, see section 1.1.

The comparison of ELLIPTA with BREEZHALER will be summarized by an odds ratio. The proportion of participants who make at least one critical error in each inhaler will be analysed using an exact conditional logistic regression model with participant as fixed strata with inhaler, and period as fixed effects. To account for very small or zero frequency counts, an exact test has been specified. In case of period effects, period has been included in the model as a fixed effect (Mehta, et al., 1995). The odds ratio of ELLIPTA relative to BREEZHALER together with the 95% confidence interval and two-sided p-value will also be presented.

Superiority will be declared based on a significance level at the two-sided 5% level.

Residual vs. Fitted plots will be generated to help assess the constant variance assumption. Deviance and Pearson goodness of fit statistics from the model will be examined to help assess the null hypothesis that the model is an adequate fit to the data.

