4.3.1.7. Willingness to continue with the inhaler

Willingness to continue with the inhaler will be measured on a VAS scale between 0 ^{CCI}
 ^{CCI} to 100 ^{CCI} The difference in means between the ELLIPTA and BREEZHALER inhaler will be presented with 95% CIs and a comparison made between the inhalers (ELLIPTA vs. BREEZHALER) using a paired t-test. The mean, standard deviation, minimum and maximum will also be presented for each inhaler. Histograms and QQ plots will be generated to assess the normality assumption.

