4.3.1.8. Preference questionnaire

For the endpoint of participants who expressed a preference on attributes from the preference questionnaire, the population summary measure is the number and percentage of participants who prefer the respective inhaler overall (ELLIPTA, BREEZHALER or no preference). A comparison will be made between the inhalers (ELLIPTA vs. BREEZHALER) using Prescott's test, where participants who select "no preference" included as uninformative. This analysis will be performed for the following variables as indicated by the participant's preference:

- a) Preferred inhaler, overall.
- b) Preference based on the number of steps to take the medication.
- c) Preference based on the time needed to take the medication.
- d) Preference based on how easy the inhaler is to use.
- e) Preference based on the size of the inhaler.
- f) Preference based on the comfort of the mouthpiece.
- g) Preference based on the ease of opening the inhaler.

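### The willingness-to-continue VAS is compared by a paired t-test that leaves period out: valid with balanced sequences, but less precise than it need be

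*SAP*

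**What the plan says.** SAP 4.3.1.7 presents the difference in mean VAS between the inhalers with a 95% CI, and "a comparison made between the inhalers (ELLIPTA vs. BREEZHALER) using a paired t-test". Protocol 9.4.2 agrees: "A paired t-test will be performed comparing the mean". The summary in SAP Table 2 (Secondary 8) is shorter: "A t-test will be performed". None of the three mentions period or sequence.

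The rating is given once per inhaler. Protocol 8.1.4 places it "After completion of the critical errors assessment for each inhaler and the ease of use questionnaire for that inhaler". Under Protocol 4.1 both inhalers are assessed at the same visit in randomised order, with an optional break between them, so the second rating always follows experience of the first inhaler.

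Elsewhere the plan allows for order. SAP 4.2.2 says of the primary model: "In case of period effects, period has been included in the model as a fixed effect". SAP 4.3.1.8 says of the preference items: "A comparison will be made between the inhalers (ELLIPTA vs. BREEZHALER) using Prescott's test". Prescott's test uses the randomised sequence by construction, although the SAP does not spell this out. In contrast, the McNemar test for further instruction (SAP 4.3.1.4) and the McNemar tests for the six ease-of-use items (SAP 4.3.1.6) have no allowance for period.

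**The concern.** In a two-period crossover, ratings may shift between the first and second period whichever inhaler is rated. In ELLIPTA-first participants that shift is added to the ELLIPTA-minus-BREEZHALER difference; in BREEZHALER-first participants it is subtracted. A paired t-test pools both groups, so the gap between the two sequence means enters the standard deviation as though it were random variation.

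Two things are at stake. With equal sequences, the interval is wider and power lower than the design allows. With unequal sequences, part of the period shift also stays in the estimate. The plan already guards against a period shift in its primary model and gives no reason for leaving the VAS unguarded.

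**Working it through.** **Inputs.** N = 114 (Protocol 9.2, SAP 5). This figure reproduces for the primary endpoint: (1.960 + 1.282)^2 × 2.785^2 / ln(0.3)^2 = 56.2, rounded up to 57 per sequence, and 2 × 57 = 114. The allocation ratio is not stated, so 57/57 is assumed. The documents give no SD, expected difference, period effect or power for the VAS. The values below are therefore assumptions: SD of within-participant differences 20, 25 or 30 points, period effect 5, 10 or 15 points, true difference 7 points.

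**Step 1: interval width.** Let the period effect be π (period 1 minus period 2) and the SD of differences within a sequence be σ. The ELLIPTA-minus-BREEZHALER difference has mean δ + π in ELLIPTA-first participants and δ − π in BREEZHALER-first participants. At 57/57 the paired test therefore sees variance of about σ² + π², and the period-adjusted test sees σ². The ratio of widths is sqrt(1 + (π/σ)²).

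| σ | π = 5 | π = 10 | π = 15 |
|---|---|---|---|
| 20 | +3% | +12% | +25% |
| 25 | +2% | +8% | +17% |
| 30 | +1% | +5% | +12% |

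At σ = 25 the variance ratios are 650/625 = 1.04, 725/625 = 1.16 and 850/625 = 1.36; their square roots are 1.020, 1.077 and 1.166.

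**Step 2: power at σ = 25, δ = 7.** At 57/57 the mean difference has true standard error 25/√114 = 2.34 under either analysis. The tests differ in the half-width that the mean must exceed:

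- adjusted: 1.9814 × 2.34 = 4.64; (7 − 4.64)/2.34 = 1.01, power 84%
- paired, π = 5: 1.9812 × √(650/114) = 4.73; (7 − 4.73)/2.34 = 0.97, power 83%
- paired, π = 10: 1.9812 × √(725/114) = 5.00; (7 − 5.00)/2.34 = 0.85, power 80%
- paired, π = 15: 1.9812 × √(850/114) = 5.41; (7 − 5.41)/2.34 = 0.68, power 75%

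Simulation agrees (84.4% adjusted; 83.4%, 80% and 75% paired). At π = 10, power paired v adjusted is 93% v 96% at σ = 20 and 66% v 69% at σ = 30. With no period effect the two tests have equal power (84.1% each at σ = 25).

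**Step 3: type I error at 57/57.** In 200,000 simulated trials per setting with no true difference, the paired test rejected in 4.9%, 4.3%, 2.9% and 0.6% of trials at period effects of 0.1, 0.25, 0.5 and 1.0 SD. The adjusted test stayed at about 5%. The paired test is conservative.

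**Step 4: unequal sequences.** Bias of the paired estimate = π × (n1 − n2)/N. For π = 10 this is 10 × 2/114 = 0.18 points at 58/56 and 10 × 6/114 = 0.53 at 60/54. At 60/54 with a period effect of 0.5 SD, type I error was 3.5%, still below nominal. It rose above 5% only with marked imbalance: at 65/49 and 0.5 SD, bias is 0.5 × 16/114 = 0.070 SD and type I error 7.6%, against 5.0% adjusted.

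**Step 5: what adjustment does not do.** If one sequence carries over 5 points more than the other, both estimates are biased by 5/2 = 2.5 points. With σ = 25, π = 10 and no true difference, false rejection is 12.9% paired and 18.5% adjusted. A period term does not remove unequal carry-over.

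**The case against.** The strongest reply is that nothing here is wrong. With balanced sequences the paired t-test is a valid analysis of a secondary endpoint for which the trial was not sized, and SAP 4.3.1.7 already gives a CI and normality checks. That stands.

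The size of the loss depends on inputs that the documents do not give. At a 5-point period effect, power falls by about one percentage point or less at each SD considered. If the true difference is 10 points rather than 7, a 10-point period effect moves power only from 98.8% to 98.3% at SD 25. That also stands: a material loss needs a modest true difference together with a sizeable period effect.

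The VAS is not an outlier either. With one McNemar test for further instruction and six for ease of use, it is one of eight paired comparisons without period. The short wording in SAP Table 2 is best read as shorthand, since the two fuller descriptions both say paired.

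What survives is narrow. The randomised sequence is already recorded, using it costs almost nothing, and the plan does use it for the primary and preference analyses.

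**Conclusion.** The point holds as a nearly free gain in precision and consistency. At 57/57 the paired test is unbiased and conservative. Under the assumed SD of 25 the interval is 2% to 17% too wide over period effects of 5 to 15 points. The power loss is about 1 point at a period effect of 5, 4 at 10 and 9 at 15, for an assumed difference of 7. If there is no period effect, nothing is lost.

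A reader might infer two stronger things, and the documents support neither. The first is that the VAS test risks a false positive from period. That needs clearly unequal sequences, and the plan expects no withdrawals. The second is that learning from the first inhaler undermines the primary comparison. The plan states that "no carry over effect is assumed based on previous evidence", and Protocol 4.2 cites earlier experience: "No carry-over effects were demonstrated when using this design previously". Whether that evidence suffices cannot be judged from the documents, but they contain nothing that shows unequal learning. The primary model includes period, and SAP 4.3.2.2 already tabulates participants with errors by sequence within each period.

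**What to change.** In SAP 4.3.1.7, SAP Table 2 (Secondary 8) and Protocol 9.4.2, replace the paired t-test with:

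> Within-participant period differences (period 1 minus period 2) will be compared between sequences with a two-sample t-test; half of (mean in the ELLIPTA-first sequence minus mean in the BREEZHALER-first sequence) estimates ELLIPTA minus BREEZHALER and will be presented with its 95% CI.

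An equivalent model with participant, inhaler and period would serve as well. If the protocol is not amended, record the change as a row in SAP Table 3. Keep the direction of subtraction explicit, because it fixes the sign of the estimate. Add a sentence saying that the analysis allows for a period effect common to both sequences and not for unequal carry-over.

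The cost is one sentence with matching edits and one degree of freedom (113 to 112; critical t from 1.9812 to 1.9814). At 57/57 the point estimate is unchanged. The McNemar tests are left as they are.

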4.3.1.8. Preference questionnaire

For the endpoint of participants who expressed a preference on attributes from the preference questionnaire, the population summary measure is the number and percentage of participants who prefer the respective inhaler overall (ELLIPTA, BREEZHALER or no preference). A comparison will be made between the inhalers (ELLIPTA vs. BREEZHALER) using Prescott's test, where participants who select "no preference" included as uninformative. This analysis will be performed for the following variables as indicated by the participant's preference:

- a) Preferred inhaler, overall.
- b) Preference based on the number of steps to take the medication.
- c) Preference based on the time needed to take the medication.
- d) Preference based on how easy the inhaler is to use.
- e) Preference based on the size of the inhaler.
- f) Preference based on the comfort of the mouthpiece.
- g) Preference based on the ease of opening the inhaler.

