Once the error assessment of the second inhaler has been completed the participant will complete the ease-of-use questionnaire for this device ([Appendix 4](#)) followed by participant completion of the VAS on their willingness to continue with this inhaler ([Appendix 5](#)).

If required, another period of up to 30 min for a break would be allowed followed by the participant completing one of the two versions of the preference questionnaire ([Appendix 6](#)), as per randomization sequence.

Two versions of the inhaler preference questionnaire (See [Appendix 6](#)) are provided to minimize any potential bias introduced from the order in which the inhalers are taken in relation to the order the inhalers are assessed by the participant in each questionnaire. The version of each questionnaire to be completed by each participant is determined by the sequence arm they are randomly assigned to at Visit 1 (see [Table 1](#)).

Further details are available in the study schematic in Section [1.2](#) and the assessments to be performed are detailed in the schedule of activities (SOA) in Section [1.3](#) and in study assessments Section [8](#).

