6.3. Measures to Minimize Bias: Randomization and Blinding

This is an open-label study; however, the specific intervention to be taken by a participant will be assigned using an IVRS/IWRS. The site will contact the IVRS/IWRS prior to the start of study intervention administration for each participant. The site will record the intervention assignment on the applicable electronic case report form (eCRF), if required. Potential bias will be reduced by the following steps: by randomizing the order of intervention and the preference questionnaire versions that will be answered by the participants as per [Table 1](#).

Table 1 Randomization Schedule

Sequence Arm	Part 1	Part 2	Preference Questionnaire (versions)
A	ELLIPTA	BREEZHALER	1
B	ELLIPTA	BREEZHALER	2
C	BREEZHALER	ELLIPTA	1
D	BREEZHALER	ELLIPTA	2

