10.6. Appendix 6: Preference Questionnaires

[figure not shown]
Version 1 - Sequence A (ELLIPTA BREEZHALER) and Sequence C (BREEZHALER ELLIPTA)

[figure not shown]
CCI - This section contained Clinical Outcome Assessment data collection questionnaires or indices, which are protected by third party copyright laws and therefore have been excluded.

Version 2 - Sequence B (ELLIPTA BREEZHALER) and Sequence D (BREEZHALER ELLIPTA)

CCI - This section contained Clinical Outcome Assessment data collection questionnaires or indices, which are protected by third party copyright laws and therefore have been excluded.

10.7. **Appendix 7: ADEs, SADEs, and Device Deficiencies: Definition and Procedures for Recording, Evaluating, Follow-up, and Reporting in Medical Device Studies**

- The definitions and procedures detailed in this appendix are in accordance with ISO 14155 and European Medical Device Regulation (MDR) 2017/745 for clinical device research (if applicable).
- Both the investigator and the sponsor will comply with all local medical device reporting requirements for medical devices.
- The detection and documentation procedures described in this protocol apply to all GSK medical devices provided for use in the study (see Section 6.1.1 for the list of GSK medical devices).

10.7.1. **Definition of ADE**

ADE Definition

 • An adverse device effect (ADE) is an AE related to the use of an investigational medical device. This definition includes any AE resulting from insufficient or inadequate instructions for use, deployment, implantation, installation, or operation, or any malfunction of the investigational medical device as well as any event resulting from use error or from intentional misuse of the investigational medical device.

10.7.2. **Definition of SADE**

A SADE is any serious ADE that:
a. Led to death
b. Led to serious deterioration in the health of the participant, that either resulted in:

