Design Features	
 This is a randomized, multi-centre, open label, placebo inhaler-handling study with a 2x2 complete block crossover design to study critical errors, overall errors, training/teaching time, ease-of-use and willingness to continue and preference attributes of two dry powder inhalers: ELLIPTA and BREEZHALER. Each participant will be randomized to one of the four groups: ELLIPTA followed by BREEZHALER or BREEZHALER followed by ELLIPTA and further refined by assignment of the preference questionnaire version (i.e. version 1 or 2). The study involves two visits which can be completed on the same day. Visit 1 may be completed up to 30 days after visit 0. A participant is considered to have completed study treatment if demonstration of both inhalers has been completed on Day 1 (Visit 1). A participant is considered to have completed the study if all assessments have been completed on Day 1 (Visit 1). Period 1 is complete once demonstration has been completed on the first inhaler after reading the PIL (or receiving up to 3 further HCP instructions), after completing the "Ease of Use" questionnaire and after completing the "Willingness to Continue" question. Period 2 is complete once demonstration has been completed on the second inhaler after reading the PIL (or receiving up to 3 further HCP instructions), after completing the "Ease of Use" questionnaire and after completing the "Willingness to Continue" question. Participants may take up to a 30-minute break between period 1 and period 2. 				

Overview of Study Design and Key Features	
	
 Participants may take up to a 30-minute break after period 2 prior to completion of the preference questionnaire. A participant may withdraw from the study at any time at his/her own request or may be withdrawn at any time at the discretion of the investigator for safety, behavioural, or compliance reasons.

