Study intervention	
 This is a placebo inhaler device study. Participants will receive both inhalers (ELLIPTA and BREEZHALER) on day 1 (Visit 1). Discontinuation of study intervention corresponds to withdrawal from the study since each inhaler is only available on a single day. If a participant withdraws during the interval between screening (V0) and Visit 1, there are no assessments that would need to be completed following withdrawal. A participant can also withdraw following randomization. In such cases, the participant may be asked to provide the reason for discontinuation which needs to be documented.
Study intervention Assignment	
 This study will randomly assign 114 adult asthma participants aged ≥ 18 years with mild to moderate asthma, naïve to both DPI inhalers (ELLIPTA and BREEZHALER). Each participant will be randomized to inhaler sequence (ELLIPTA/BREEZHALER or BREEZHALER/ELLIPTA) and to the preference questionnaire (version 1 or version 2). There will be a total of four possible groups: 
 ELLIPTA/BREEZHALER/preference questionnaire version 1 ELLIPTA/BREEZHALER/preference questionnaire version 2 BREEZHALER/ELLIPTA/preference questionnaire version 1 BREEZHALER/ELLIPTA/preference questionnaire version 2 The randomisation schedule will be generated using the GSK validated randomisation software RandAll NG. Eligible participants will be assigned to study treatment randomly using RAMOS NG, an Interactive Web Response System (IWRS).
Interim Analysis	No interim analysis of data is planned for this study.

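### The preference analysis pools over the randomised questionnaire version; stratifying Prescott's test by whether listing order matches order of use is a free, low-severity improvement

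*SAP*

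**What the plan says.** Protocol 4.1 explains that there are two versions of the preference questionnaire "to minimize any potential bias introduced from the order in which the inhalers are taken in relation to the order the inhalers are assessed". Protocol 6.3 lists this among the steps against bias: "by randomizing the order of intervention and the preference questionnaire versions that will be answered by the participants". Table 1 of the protocol crosses inhaler order with version:

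- A: ELLIPTA first, version 1
- B: ELLIPTA first, version 2
- C: BREEZHALER first, version 1
- D: BREEZHALER first, version 2

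SAP 1.2 repeats the structure ("There will be a total of four possible groups") and calls the study a "2x2 complete block crossover design". Neither document gives an allocation ratio or a block size.

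The analysis in SAP 4.3.1.8 is one sentence, applied to seven attributes: "A comparison will be made between the inhalers (ELLIPTA vs. BREEZHALER) using Prescott's test", with no-preference answers kept as uninformative. Protocol 9.4.2 matches it. Version is not named as a stratum, covariate or summary variable in either place. SAP 4.5.1 plans no subgroup analyses, and SAP 4.7 lists no related change.

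**The concern.** Prescott's test compares the two inhaler sequences, so it sets A+B against C+D. That deals with order of use. Listing order, the second factor the sponsor chose to randomise, is left out of the analysis. A factor that is randomised because it may move the outcome is normally carried into the analysis. If it is not, whatever it explains stays in the variance of the test. The possible cost is a test with true size below 5% and some power forgone on each of seven preference comparisons. In addition, the SAP text itself plans no display showing whether listing order made a difference.

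**Working it through.** **The plan's own figure.** No power is stated for the preference test. The stated 114 is for the primary endpoint and reproduces: (1.960 + 1.282)² × 2.785² / (ln 0.3)² = 10.51 × 7.756 / 1.450 = 56.2, rounded up to 57 per sequence, times 2 = 114. It fixes the sample size used here and has no other bearing on the point.

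**Set-up.** Score Y = +1 (prefers ELLIPTA), 0 (no preference), −1 (prefers BREEZHALER). Let p0 be the share with no preference and θ the average of Y. Let v be a listing effect that moves the mean of Y to θ + v in one version and θ − v in the other. With p0 fixed, v equals the gap between versions in the proportion preferring ELLIPTA. Which version lists which inhaler first is redacted, but the result does not depend on it.

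Prescott's test works on first-used versus second-used, so Z = Y in A and B, and Z = −Y in C and D. The arm means of Z are:

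- A: θ + v
- B: θ − v
- C: −(θ + v)
- D: −(θ − v)

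**Bias.** With equal arms, the mean of A+B minus the mean of C+D is 2θ. The listing effect cancels.

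**Variance W used by each test, per participant.**

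- Pooled: the overall mean of Z is 0, so W = 1 − p0.
- Stratified by version, {A, C} and {B, D}: each stratum mean is 0, so W is still 1 − p0. Nothing is gained.
- Stratified by whether listing order matches order of use, {A, D} and {B, C}: the stratum means are +v and −v, so W = 1 − p0 − v².

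The actual within-arm variance is 1 − p0 − θ² − v².

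**Formulas, balanced arms.**

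- Null size of the pooled test = 2 × {1 − Φ(1.96 × √[(1 − p0)/(1 − p0 − v²)])}
- Power = Φ{(2θ/√(2W/57) − 1.96) × √[W/(1 − p0 − θ² − v²)]}

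**Inputs.** N = 114 (SAP 1.2), two-sided 5% (SAP 4.3.1). Assumed, because the documents give no figure: average preference 55% / 13% / 32%, so θ = 0.23 and p0 = 0.13, and v as tabulated.

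Example at v = 0.32:

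- Size: √(0.87/0.7676) = 1.065; 1.96 × 1.065 = 2.087; two-sided tail 3.7%.
- Pooled power: 0.46/√(0.87 × 2/57) = 2.633; (2.633 − 1.96) × √(0.87/0.7147) = 0.742; 77%.
- Stratified power: 0.46/√(0.7676 × 2/57) = 2.803; (2.803 − 1.96) × √(0.7676/0.7147) = 0.874; 81%.

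| Version gap (points) | Pooled null size, formula | Pooled power | Stratified power |
|---|---|---|---|
| 0 | 5.0% | 76% | 76% |
| 10 | 4.9% | 76% | 76% |
| 20 | 4.5% | 76% | 78% |
| 32 | 3.7% | 77% | 81% |
| 47 | 2.3% | 79% | 88% |

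The power columns are from simulation (arms 29/28/28/29, 400,000 runs per cell); the formula agrees to within about one point. Simulated null size was 4.9%, 4.5%, 3.6% and 2.3% at gaps of 10, 20, 32 and 47 points. A separate simulation gave 4.8%, 4.3%, 3.6% and 2.2%, with pooled power of 80% in the last row. Null size with strata {A, D} and {B, C} stayed at about 5% throughout. Stratifying by version alone matched the pooled test to within 0.2 points.

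**Other assumptions.**

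- *p0 = 0.20, θ = 0.25.* Pooled size is 4.9%, 4.5%, 3.8% and 2.8% at v = 0.1, 0.2, 0.3 and 0.4. Power pooled v stratified is 86.5% v 87.7%, 87.5% v 90.1% and 88.9% v 93.4% at v = 0.2, 0.3 and 0.4.
- *Version allocated by simple randomisation, same p0 and θ.* Pooled size stays at about 5.0%, and power is 85.5% v 87.1% at v = 0.2 and 85.6% v 93.0% at v = 0.4.
- *Listing effect present only when listing order matches order of use, same p0, balanced arms.* Pooled size is 4.9%, 4.7% and 4.4% at v = 0.2, 0.3 and 0.4.

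**The case against.** The strongest reply is that the design has already done what the protocol asked of it. Version was randomised to limit bias, crossing it with sequence achieves that, and nothing in the protocol promises a version-adjusted analysis. The plan therefore does not contradict itself. Because the cost depends on v², a gap of 10 points is invisible and one of 20 points costs about two points of power. The documents give no reason to expect a gap of 32 or 47 points. Preference is one of nine secondary estimands, and SAP 2.1 makes no multiplicity adjustment.

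All of that stands, and it limits the severity. It does not give a reason to leave out a stratum that is already recorded.

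Three stronger readings are tempting and are not supported:

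- *The planned test loses power as the listing effect grows.* With average preference held fixed, pooled power does not fall; it moves from 76% to about 79%. The planned test only forgoes a gain.
- *The size is below 5% whatever the allocation.* That needs version balanced within sequence. The four-arm schedule and the complete-block wording suggest balance, but no ratio or block size is stated.
- *The study report will never show a version effect.* SAP section 1 leaves data displays to the Output and Programming Specification, which is not available here. All that can be said is that neither document plans such a display.

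**Conclusion.** The point holds as a low-severity, no-cost improvement. SAP 4.3.1.8 and Protocol 9.4.2 leave out a factor that the trial randomises because it may affect the answer. The effect on inference is one-sided: the comparison is unbiased, and the size did not exceed 5% beyond simulation error in any scenario run. A reader might infer that ignoring version could produce a spurious preference for one inhaler; the calculation shows that it cannot.

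Under the assumed 55% / 13% / 32% preference, the power forgone runs from under 1 point at a 10-point gap to about 9 points at 47. This rests on assumed preference shares and an assumed listing effect. The size result also rests on balanced arms. The versions are taken to differ in listing order on the strength of Protocol 4.1, because the questionnaires themselves are redacted.

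**What to change.** Before database lock, add one sentence to SAP 4.3.1.8, with an entry in SAP 4.7 because Protocol 9.4.2 describes the unstratified test. It should say that Prescott's test is stratified by whether the inhaler listed first in the assigned version is also the one used first, with strata {A, D} and {B, C}. In practice this is a row-mean-score Cochran-Mantel-Haenszel test of inhaler sequence by preference, with preference coded as first-used, none or second-used. Do not stratify by version alone, which leaves size and power as they are.

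Also specify a table of preference by version for each of the seven attributes. If only one change is accepted, this table is the minimum.

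The cost is a sentence, one stratification variable and one table. The arm is already recorded. If there is no listing effect, the stratified and pooled tests have the same power with balanced arms (76% in the example above). Stating the change now avoids the appearance of having chosen the analysis after seeing the results.
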